4.1 Inclusion criteria

- (1) Women aged > 18 years;
- (2) Histologically confirmed endometrial cancer;
- (3) Recurrent or advanced endometrial cancer with at least one treatment with systemic platinum-based chemotherapy;
 - Low chance of a cure for recurrent endometrial cancer with surgery and/or radiotherapy and failure of at least one treatment with systemic platinum-based chemotherapy after recurrence.
 - Newly diagnosed advanced endometrial cancer persisting after standard treatment with surgery \pm radiochemotherapy and at least one treatment with systemic platinum-based chemotherapy.
- (4) Objectively measurable lesions based on RECIST 1.1 criteria and at least one target lesion;

- In principle, lesions in the field of previous radiotherapy are considered as non-target lesions unless there is radiological evidence of progression or a biopsy with progression within 90 days after radiotherapy.
- (5) Eastern Cooperative Oncology Group (ECOG) score of 0–2;
- (6) Expected survival >3 months;
- (7) Major organ function fulfills the following criteria (correction of the following parameters and supportive treatment are allowed 1 week before enrollment);
 - Absolute neutrophil count $\geq 1.5 \times 10^9/L$, platelet count $\geq 70 \times 10^9/L$, hemoglobin $\geq 80g/L$
 - Alanine transaminase (ALT) and aspartate transaminase (AST) $\leq 2.5 \times$ upper limit of normal (ULN) ($<5 \times$ for patients with liver metastases) and total bilirubin $\leq 1.5 \times$ ULN
 - Serum creatinine $\leq 1.5 \times$ ULN
 - International normalized ratio (INR) $<1.5 \times$ ULN
 - Proteinuria $\leq (+)$
 - Thyroid-stimulating hormone (TSH) $\leq 1 \times$ ULN (measure FT3 and FT4 if TSH abnormal; subjects with normal FT3 and FT4 can be enrolled)
- (8) Voluntarily signed informed consent form.

4.2 Exclusion criteria

- (1) Presence of carcinosarcoma in pathology specimen (including malignant mixed Müllerian tumor, uterine leiomyosarcoma, and endometrial stromal sarcoma);
- (2) Received other antineoplastic drugs within 4 weeks before the first dose;
- (3) Underwent major surgery within the past 28 days or expected to undergo major surgery during the study period;
- (4) Received radiotherapy 21 days before drug administration (palliative radiotherapy within 2 weeks for subjects with bone metastases);
- (5) Prior therapy with anti-PD-1 antibody;
- (6) Grade >1 unresolvable and persistent adverse reaction caused by previous treatment (except for alopecia, grade >2 neurotoxicity);
- (7) Patients currently on immunosuppressants or systemic steroid treatment for immunosuppression (dose >10 mg/day prednisone or another equivalent steroid) and still on immunosuppressive treatment within 2 weeks before enrollment.
- (8) Other malignant tumors in the last 5 years (except for adequately treated *in situ* malignant tumors, such as breast cancer, bladder carcinoma, cervical carcinoma *in situ*, basal cell carcinoma, or squamous cell carcinoma of the skin);

- (9) A history of psychotropic substance abuse that the subject is unable to discontinue or subjects with mental disorders;
- (10) Central nervous system disorder: including epilepsy not controlled by drugs and symptomatic brain metastases;
- (11) A digestive disorder that affects drug absorption (such as atrophic gastritis).
- (12) Patients with an active ulcer, intestinal perforation, or unresolved intestinal obstruction, and patients with digestive tract perforation within 28 days before enrollment;
- (13) Hypertension not controlled by drugs (blood pressure >140/90 mmHg after adequate conventional treatment);
- (14) Severe cardiovascular disease: unstable angina, myocardial infarction, class III–IV heart failure (NYHA criteria), and grade 2 and above peripheral vascular disorder within 6 months before enrollment;
- (15) Severe arrhythmia requiring drug control and a clinically significant prolonged QT interval (>470 ms);
- (16) Subjects with active bleeding or a bleeding tendency;
- (17) Subjects with arterial/venous thrombosis within 6 weeks before enrollment, such as cerebrovascular events (including stroke, transient ischemic attacks, subarachnoid hemorrhage), deep vein thrombosis, and pulmonary embolism;
- (18) Active infection, such as HIV/AIDS or other severe infections;
- (19) Any active autoimmune disease or history of autoimmune disease (including but not limited to autoimmune hepatitis, interstitial pneumonia, hepatitis, enteritis, nephritis, hyperthyroidism, hypophysitis, vasculitis, uveitis) or patients who require systemic steroid treatment and/or immunosuppressant treatment (such as asthma requiring steroid-bronchodilator treatment);
- (20) Received a live vaccine within 30 days before the first dose;
- (21) Known allergy to any of the study drugs;
- (22) Women of child-bearing age must have a negative pregnancy test and follow strict contraceptive measures during the trial;
- (23) Patients deemed unsuitable for enrollment by the investigator.

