Exclusion criteria	
 1. Presence of carcinosarcoma in pathology specimen (including malignant mixed Müllerian tumor, uterine leiomyosarcoma, and endometrial stromal sarcoma); 2. Received other antineoplastic drugs 4 weeks before the first dose; 3. Underwent major surgery in the past 28 days or expected to undergo major surgery during the study period; 4. Received radiotherapy 21 days before drug administration (palliative radiotherapy within 2 weeks for subjects with bone metastases); 5. Prior therapy with anti-PD-1 antibody; 6. Grade > 1 unresolvable and persistent adverse reaction caused by previous treatment (except for alopecia and grade > 2 neurotoxicity); 7. Patients currently on immunosuppressants or systemic steroid treatment (dose > 10 mg/day prednisone or another equivalent steroid) and still on immunosuppressive treatment 2 weeks before enrollment. 8. Other malignant tumors in the last 5 years (except for adequately treated in situ malignant tumors such as breast cancer, bladder carcinoma, cervical carcinoma in situ, basal cell carcinoma, or squamous cell carcinoma of the skin); 9. Psychotropic substance abuse that the subject is unable to discontinue or subjects with mental disorders; 10. Central nervous system disorders including uncontrolled epilepsy and symptomatic brain metastases;

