4.3. Removal criteria

Subjects enrolled in this trial who meet one of the following criteria will be removed:

(1) Enrolled subjects who do not satisfy the inclusion criteria/satisfy the exclusion criteria and are wrongly enrolled.

(2) Subjects with serious protocol violations.

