6.2. IBI308 (sintilimab) dose modification

Sintilimab dose modification is not permitted during the entire study. Table 3 shows the principles of suspension and permanent discontinuation for sintilimab. If the dose delay occurs during sintilimab treatment (3 weeks per cycle), all future dosing dates will be delayed to ensure that the dosing interval between sintilimab treatment cycles is 21 ± 3 days.

Table 2. Dose modification protocol for IBI308 (sintilimab)-related toxicity

Sintilimab-related adverse events	Severity	Dose modification
Hematological toxicity	Grade 1–3	Drug discontinuation not required
	Grade 4	Drug interruption
Pneumonitis	Grade 2 pneumonitis	Drug interruption
	Recurrent Grade 2 to Grade 4 pneumonitis	Permanent drug discontinuation
Diarrhea/enterocolitis	Grade 2 or 3 diarrhea or enterocolitis	Drug interruption

	Grade 4 diarrhea or enterocolitis	Permanent drug discontinuation
Dermatitis	Grade 3 dermatitis	Drug interruption
	Grade 3–4 dermatitis	Permanent drug discontinuation
Impaired hepatic function	Grade 2 AST, ALT, or TBIL increased in subjects with normal baseline AST, ALT, or TBIL; $\geq 50\%$ increase in AST, ALT, or TBIL (reaching grade 2 requirement) lasting < 7 days in subjects with baseline AST, ALT, or TBIL $> \text{ULN}$.	Drug interruption
	Grade 3 or 4 AST, ALT, or TBIL increased in subjects with normal baseline AST, ALT, or TBIL; $\geq 50\%$ increase in AST, ALT, or TBIL (reaching grade 3 or 4 requirements) lasting ≥ 7 days in subjects with baseline AST, ALT, or TBIL $> \text{ULN}$.	Permanent drug discontinuation
Hypophysitis	Grade 2 hypophysitis	Drug interruption
	Grade 3–4 hypophysitis	Permanent drug discontinuation
Adrenal insufficiency	Grade 2 adrenal insufficiency	Drug interruption
	Grade 3 or 4 adrenal insufficiency	Permanent drug discontinuation
Hyperthyroidism	Grade 3–4 hyperthyroidism	Permanent drug discontinuation
Hyperglycemia	Grade 3 hyperglycemia	Drug interruption
	Grade 4 hyperglycemia	Permanent drug discontinuation
Renal impairment	Grade 2–3 increase of creatinine	Drug interruption
	Grade 4 increase of creatinine	Permanent drug discontinuation
Neurotoxicity	Grade 2 neurotoxicity	Drug interruption
	Grade 3–4 neurotoxicity	Permanent drug discontinuation
Other AEs	First occurrence of other Grade 3 AE	Drug interruption
	Second occurrence of the same Grade 3 AE	Permanent drug discontinuation

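### Exclusion 6 exempts neurotoxicity above grade 2, so as written it bars persistent grade 2 neuropathy and lets grade 3–4 through

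*Protocol*

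**What the plan says.** Section 4.2, exclusion 6, sets a general threshold for toxicity left over from earlier treatment and attaches two exceptions: "Grade >1 unresolvable and persistent adverse reaction caused by previous treatment (except for alopecia, grade >2 neurotoxicity". The synopsis, exclusion 6, repeats the rule with *and* in place of the comma: "except for alopecia and grade > 2 neurotoxicity".

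Other provisions bear on how the criterion works:

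- **Section 4.1, inclusion 3** requires prior platinum treatment of every patient: "Recurrent or advanced endometrial cancer with at least one treatment with systemic platinum-based chemotherapy". Section 1.3 names paclitaxel with carboplatin as the guideline first-line regimen.
- **Section 4.3, item 1** lists among the subjects to be removed: "Enrolled subjects who do not satisfy the inclusion criteria/satisfy the exclusion criteria and are wrongly enrolled".
- **Section 4.2, exclusion 23** leaves a general discretion: "Patients deemed unsuitable for enrollment by the investigator".
- **Section 6.2, Table 2** interrupts sintilimab for "Grade 2 neurotoxicity" and stops it permanently for "Grade 3–4 neurotoxicity".
- **Section 6.1** requires other toxicities to be at grade 0–1 or at baseline level before each dose.

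**The concern.** An exception to a toxicity exclusion normally tolerates a somewhat higher grade of a particular toxicity and then stops. Here the exception starts where such a tolerance would end. The milder case is turned away, and the more severe case is passed to the investigator's general discretion.

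This matters in this trial because the whole population has had platinum-based chemotherapy and because the authors thought neurotoxicity important enough to give it its own clause. The criterion is an operative screening rule, and following it exactly gives the wrong answer.

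Either way of running the trial has a cost. Staff who follow the text refuse grade 2 patients and have no explicit rule against grade 3–4. Staff who follow the presumed intent enrol grade 2 patients who meet an exclusion criterion as printed. Those patients are then open to removal under section 4.3 and to challenge in the per-protocol set of section 11.1, which requires conformity with the protocol.

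**Working it through.** No sample size, power or error rate is involved. The check applies the rule to each grade.

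**Rule as printed** (section 4.2 and synopsis): a patient with persistent neurotoxicity from earlier treatment is excluded if grade > 1 and not (grade > 2).

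**Rule with the exception capped at grade 2:** excluded if grade > 1 and not (grade ≤ 2), which reduces to grade > 2.

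| Persistent neurotoxicity | Grade > 1? | Excepted as printed (> 2)? | Status as printed | Status with exception ≤ 2 |
|---|---|---|---|---|
| Grade 0–1 | no | not needed | eligible | eligible |
| Grade 2 | yes | no | **excluded** | eligible |
| Grade 3 | yes | yes | **eligible** | excluded |
| Grade 4 | yes | yes | **eligible** | excluded |

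Here *eligible* means not excluded by criterion 6. The status changes at grades 2, 3 and 4, which is 3 of the 3 grades above grade 1.

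**Is it an isolated slip or a reading error?** The same sign appears in two differently worded places, and the symbols ≤ and ≥ are intact elsewhere in the eligibility sections. A lost character in both places is unlikely.

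**Does anything else in the protocol close the gap?**

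- No other exclusion names neuropathy from earlier treatment.
- The pre-dose check in section 6.1 accepts a toxicity that is at baseline level, so stable grade 3 neuropathy present at entry satisfies it.
- Table 2 concerns neurotoxicity related to sintilimab on study. It does not conflict with exclusion 6. It shows only that the protocol itself ranks grade 3–4 as more serious than grade 2.
- Exclusion 23 and the ECOG limit can add exclusions but cannot waive one. They may catch some grade 3–4 patients and do nothing for grade 2.

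**Scale of a removal, as illustration only.** One patient removed under section 4.3 would be 1/23 = 0.0435, or 4.3% of the planned sample.

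**The case against.** The best defence rests on the comma in section 4.2. The bracket "except for alopecia, grade >2 neurotoxicity" could be shorthand for a separate exclusion threshold: alopecia never excludes, and neurotoxicity excludes only above grade 2. On that reading the rule is already the sensible one. The synopsis does not allow it. There the two items are joined by *and* under a single *except*, so neurotoxicity above grade 2 is exempt exactly as alopecia is. A screening rule should not depend on the reader choosing the less literal of two readings.

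The second argument is that the practical risk is low. This is a single-centre trial, and enrolling a grade 3–4 patient would require the team to accept an absurd reading and also leave exclusion 23 unused. That is fair and limits the safety consequence, but it does not make the text right.

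The third argument is that the removal scenario is remote. It needs a team that enrols on one reading and removes on the other. Section 3.1 also puts all enrolled subjects into the efficacy analysis, and section 11.2 defines the full analysis set as all included patients. This largely stands: the 4.3% figure is conditional and is not an estimated effect on the primary endpoint.

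Finally, the protocol does not say how often residual neuropathy occurs in such patients. That is also true, and no patient count is claimed.

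**Conclusion.** The criterion is wrong as written. In both places where it appears, it excludes persistent grade 2 neurotoxicity and exempts grades 3 and 4, which reverses the order of severity for all three grades above grade 1. Nothing else in the protocol corrects it.

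That the authors meant to tolerate neuropathy up to grade 2 is an inference. It is the most plausible explanation, but the text does not state it. The conclusion that the printed rule is inverted does not depend on that inference.

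The consequence is for eligibility and patient safety. The objective response rate endpoint, the Simon two-stage boundaries, the sample size and the dose rules are unaffected. The point should be corrected, although discretionary safeguards soften its practical effect.

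**What to change.** In section 4.2, exclusion 6, and in synopsis exclusion 6, replace the bracketed exception with an explicit upper limit, for example: *except for alopecia and neurotoxicity of grade ≤2*. The investigators should confirm that grade 2 is the intended limit. Grades 0–2 are then eligible under this criterion and grades 3–4 excluded, with identical wording in both places.

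The cost is a one-line amendment made twice. Section 6.1, Table 2, the sample size and the analysis need no change.

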	
 11. A digestive disorder that affects drug absorption (such as atrophic gastritis). 12. Patients with an active ulcer, intestinal perforation, or unresolved intestinal obstruction and patients with digestive tract perforation 28 days before enrollment; 13. Uncontrolled hypertension (blood pressure >140/90 mmHg) after adequate conventional treatment; 14. Severe cardiovascular disease: unstable angina, myocardial infarction, class III–IV heart failure (NYHA criteria), and grade 2 and above peripheral vascular disorder 6 months before enrollment; 15. Severe arrhythmia requiring drug control and a clinically significant prolonged QT interval (>470 ms); 16. Active bleeding or a bleeding tendency; 17. Arterial/venous thrombosis 6 months before enrollment, such as cerebrovascular events (including stroke, transient ischemic attacks, subarachnoid hemorrhage), deep vein thrombosis, and pulmonary embolism; 18. Active infections, such as HIV/AIDS or other severe infections; 19. Any active autoimmune disease or history of autoimmune disease (including but not limited to autoimmune hepatitis, interstitial pneumonia, hepatitis, enteritis, nephritis, hyperthyroidism, hypophysitis, vasculitis, uveitis) or patients who require systemic steroid and/or immunosuppressant treatment (such as asthma requiring steroid-bronchodilator treatment); 20. Received a live vaccine within 30 days before the first dose; 21. Known allergy to any of the study drugs; 22. Women of child-bearing age must have a negative pregnancy test and follow strict contraceptive measures during the trial; 23. Patients deemed unsuitable for enrollment by the investigator.
Treatment withdrawal criteria	
 1. Subject withdraws informed consent; 2. Radiologic examination shows disease progression; 
 • Since pseudoprogression occurs with PD-1, confirmation should be performed 4–6 weeks after the first disease progression result except for

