ms). In patients on anlotinib who take antiarrhythmic drugs or have related underlying heart disease, bradycardia, and electrolyte disturbance, electrocardiography should be performed every 2–3 weeks to evaluate the QT interval.

Electrocardiography and cardiac function should be closely monitored during the dosing period. Drug interruption is recommended if a Grade 3/4 adverse reaction occurs. If a Grade 3/4 adverse reaction recurs after dosing is resumed, subsequent doses can be reduced by one level. Drug discontinuation is recommended if the adverse reaction persists. Drug discontinuation is recommended for patients who develop Grade III–IV heart failure or patients with a left ventricular ejection fraction <50% on Doppler echocardiography.

Stroke risk: Although a stroke event has yet to be observed in existing clinical trials of anlotinib, hypertension and hyperlipidemia are common adverse reactions of anlotinib and constitute a high-risk factor for stroke. Long-term use of this product may increase stroke risk. Therefore, it is recommended that blood pressure, blood lipids, and other stroke risk factors should be closely monitored in high-risk stroke patients to prevent stroke.

Epilepsy: Epilepsy was observed in patients in the anlotinib arm in clinical trials. It has not been confirmed whether this product can cause epilepsy or increase the risk of epilepsy. This product should be used with caution under the guidance of a physician for patients with a medical history of epilepsy.

Dermatotoxicity: Hand-foot-skin reaction (swelling and pain in the palms and soles or erythema of the fingers and toes) is a common adverse skin reaction with this type of drug. A Grade 1 hand-foot-skin reaction is characterized by painless mild skin changes or dermatitis (e.g., erythema, edema, hyperkeratosis); a Grade 2 hand-foot-skin reaction is characterized by painful skin changes (e.g., desquamation, blisters, bleeding, swelling, and hyperkeratosis) and affects instrumental activities of daily living; a Grade 3 hand-foot-skin reaction is characterized by severe skin changes (e.g., desquamation, blisters, bleeding, swelling and hyperkeratosis) and accompanied by pain, which affects activities of daily living.

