11.1 Definition of statistical analysis sets

Full analysis set (FAS): Analysis of all enrolled patients who took at least one dose of the drug will be performed according to the intent-to-treat principle. The last observation carried forward is used for patients whose data were not captured for the entire duration of the study.

Per-protocol set (PPS): All patients who completed 2 cycles or more of treatment, conformed to the study protocol, had good compliance, did not use prohibited drugs during the study, and whose case report forms are completed as required. No imputation will be performed for missing data. Statistical analysis of FAS and PPS are simultaneously performed for drug efficacy analysis.

Safety analysis set (SAS): All enrolled patients who had at least taken one dose of the study drug and whose safety after drug administration had been recorded. This dataset will be used for safety analysis.

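### Exclusion 17 sets a 6-month thrombosis look-back in the synopsis but 6 weeks in section 4.2, so patients with a named event about 6 to 26 weeks earlier are barred on one page and not on the other

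*Protocol*

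**What the plan says.** Exclusion 17 appears twice in version 1.0 of the protocol, with the same number and the same example events but different windows.

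- Synopsis, exclusion 17: "Arterial/venous thrombosis 6 months before enrollment, such as cerebrovascular events".
- Section 4.2(17): "Subjects with arterial/venous thrombosis within 6 weeks before enrollment, such as cerebrovascular events".

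The neighbouring exclusion 14 has a 6-month window in both places. In section 4.2 it ends with "grade 2 and above peripheral vascular disorder within 6 months before enrollment", and it also covers unstable angina, myocardial infarction and class III–IV heart failure. Exclusion 23 is a discretionary clause: "Patients deemed unsuitable for enrollment by the investigator".

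Two later provisions depend on who was properly eligible. Section 4.3(1) removes "Enrolled subjects who do not satisfy the inclusion criteria/satisfy the exclusion criteria and are wrongly enrolled". Section 11.1 defines the per-protocol set as "All patients who completed 2 cycles or more of treatment, conformed to the study protocol, had good compliance", with further conditions. For the full analysis set, section 11.1 says "Analysis of all enrolled patients who took at least one dose of the drug will be performed according to the intent-to-treat principle".

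**The concern.** Eligibility is fixed in the protocol, and screening staff check each patient against it. Here the page consulted decides whether a patient with a recent thrombotic event passes criterion 17. Nothing ranks the synopsis against the body; the only statement in the protocol about one source prevailing concerns pregnancy tests.

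Three things are at stake. The first is the consistency of a safety screen in a trial that includes a VEGFR inhibitor. The second is whether a patient admitted under the 6-week text counts as wrongly enrolled under 4.3(1). The third is whether she conformed to the protocol for the per-protocol set, which section 11.1 analyses for efficacy alongside the full analysis set.

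**Working it through.** **Design figures, for context.** An exact binomial calculation of the Simon design in section 3.1 (7 patients in stage 1, stop at 1 or fewer responses; 23 in total, reject at 5 or fewer; response rates 13% and 39%) gives alpha 0.0456 and power 0.8003. The stated 0.05 and 0.8 are reproduced. The exclusion window is not an input, so these figures do not depend on this point.

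**Width of the disagreement.**

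- 6 weeks = 6 × 7 = 42 days.
- 6 months = 365.25 / 2 = 182.6 days; 182.6 / 7 = 26.1 weeks.
- Gap = 182.6 − 42 = 140.6 days, about 20 weeks.

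| Named event before enrollment | Synopsis 17 | Section 4.2(17) |
|---|---|---|
| Up to 42 days | excluded | excluded |
| After 42 and up to about 183 days | excluded | not excluded |
| Earlier than about 183 days | not excluded | not excluded |

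Only the middle row is in conflict.

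**Which events are in the middle row.** Exclusion 14 bars myocardial infarction and peripheral vascular disorder of grade 2 or above for 6 months on both pages, so some arterial events there are excluded either way. The conflict remains for the events that criterion 17 names: stroke, transient ischemic attack, subarachnoid hemorrhage, deep vein thrombosis and pulmonary embolism.

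**Effect on the analysis sets.** Section 3.1 includes all enrolled subjects in the efficacy analysis, and section 11.2 uses the full analysis set. Under 11.1, a dosed patient belongs to that set whichever window governs. Her per-protocol status does depend on the window.

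**Related inconsistencies for the same amendment.**

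1. *Dermatitis, Table 2.* Grade 3 appears under interruption and again, within Grade 3–4, under permanent discontinuation. Other rows do not settle it. Hypophysitis, adrenal insufficiency and neurotoxicity stop permanently from Grade 3; diarrhea/enterocolitis, hyperglycemia, creatinine and a first other Grade 3 event are interrupted at Grade 3.
2. *Viral load.* Table 1 footnote 10 asks for a test every 3 weeks in hepatitis-positive subjects; the Table 1 row and section 8.2 ask for one every 2 cycles (42 days). Over the 24-month sintilimab maximum (730 days) that is 730 / 21 = 34.8 against 730 / 42 = 17.4 tests.
3. *Withdrawal for serious adverse events.* Section 4.4(3) makes withdrawal mandatory on any serious adverse event, and 9.5.1 counts an adverse event that requires hospitalization as serious. Section 6.1 lets the other drug continue when one is permanently stopped. The synopsis list has no such item; intolerable toxicity and investigator judgement are the nearest.

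**The case against.** The strongest reply is that the windows are nested. A site that applies 6 months breaches neither page, and exclusion 23 also lets the investigator decline a patient in the gap. This stands: it would be wrong to infer that no consistent practice is possible. But exclusion 23 is case-by-case discretion, and the 6-week text by itself lets through a patient whom the synopsis bars.

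Second, the consequence for the analysis is small. This also stands. A reader might infer that removal under 4.3 alters the primary result or the stage 1 decision. Sections 3.1, 11.1 and 11.2 keep enrolled, dosed patients in the full analysis set, and nothing ties the stage 1 rule to the per-protocol set. Any shift in the per-protocol response rate would need an assumed number of affected patients and of responders, and the documents supply neither.

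Third, a reader might infer that the 6-week window is unsafe. The protocol does not show that. Section 6.5 says "Although a stroke event has yet to be observed in existing clinical trials of anlotinib", adds that long-term use may raise the risk, and advises monitoring of high-risk patients. Its stroke paragraph does not address deep vein thrombosis or pulmonary embolism.

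Fourth, a reader might take exclusion 14 as proof that 6 months was intended. It covers other conditions and does not settle the intent.

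A statistical analysis plan, not at hand, could define per-protocol handling. It could not settle which eligibility window the site applies.

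**Conclusion.** The contradiction holds as a matter of text. For the named events, criterion 17 gives opposite answers over about 141 days of look-back, roughly weeks 6 to 26 before enrollment. This reads the synopsis phrase as any time in the 6 months before enrollment.

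The practical effect is confined to the safety screen, wrongly-enrolled status and per-protocol membership, and it arises only if a patient is enrolled on the 6-week text. The number of such patients is unknown. The point should be fixed because the rule is wrong as written and the correction is cheap; it does not threaten the trial's main inference. The dermatitis overlap and the viral-load conflict are also genuine, but they concern dosing and monitoring rather than eligibility.

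**What to change.** Write *within 6 months before enrollment* in both synopsis exclusion 17 and section 4.2(17). This is the more cautious choice and matches the window in exclusion 14; the clinical lead should confirm it. State that anyone already dosed under the 6-week text stays in the full analysis set, and state whether she counts as protocol-conforming for the per-protocol set.

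In the same amendment:

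1. Make the Table 2 dermatitis rows non-overlapping at Grade 3. The clinical lead should choose, since the table follows both patterns.
2. Use one viral-load interval in footnote 10, the Table 1 row and section 8.2.
3. If 4.4(3) is also amended, limit it to serious adverse events that require permanent discontinuation of both study drugs. Tying it to discontinuation of either drug would leave the conflict with 6.1 in place.

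The cost is one amendment, reported to the ethics committee as section 12.4 requires, and a notice to the single site. No patients are added. The downside of 6 months is that a few patients admissible under section 4.2 would be excluded. Choosing the 3-week viral-load interval would roughly double those tests against the 2-cycle schedule, for hepatitis-positive subjects only.
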